**METHODS** 

**Patients** 

Study participants must fulfill the following eligibility criteria: 1) early ARDS (establishment of the diagnosis within the preceding 72 hours) according to the criteria of the American-European Consensus Conference (18), 2) severe oxygen disturbance [defined as ratio of partial pressure of arterial oxygen (PaO2) to inspired oxygen fraction (FiO2)<150mmHg, while they are on CMV with positive endexpiratory pressure (PEEP) set at ≥8cmH2O, 3) age 18-75 years, body weight >40 Kg, and 4) absence of a) severe air leak (more than one chest tubes per hemithorax with persistent air leak for more than 72 hours), b) systolic blood pressure lower than 90 mmHg, despite maximum support with fluids and vasopressor drugs (i.e., norepinephrine infusion rate exceeding 0,5 µg/kg/min, c) significant heart disease (e.g. ejection fraction lower than 40%, history of pulmonary edema and active ischemic disease or myocardial infarction), d) severe chronic obstructive pulmonary disease (COPD) or asthma (e.g. previous admission for COPD/asthma, chronic treatment with corticosteroids for COPD/asthma, and chronic CO2 retention more than 50 mmHg), e) intracranial pathology with intracranial pressure >20mmHg, not responsive to conservative treatment (e.g. hemorrhage, head injury, tumor, infection or acute ischemic stroke), f) chronic interstitial lung disease with bilateral lung infiltrates, g) lung biopsy or incision during the current admission, h) previous lung transplantation or bone marrow transplantation, i) pregnancy, j) immunosuppression, and k) participation in another clinical study.

2

Randomization will result in assignment to either the control group (treatment with CMV) or the HFO-TGI group (treatment with CMV and HFO-TGI sessions, as described in the following paragraphs). The randomization technique will comprise the use of computer-generated sequence(s) of random numbers and a "sealed envelope technique", in order to achieve concealment until patient study entry.

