After considering the above-mentioned factors of study feasibility, we propose to conduct the trial in 2 periods: a single-center first period of at least 50 patients (average estimate=52 patients, maximum=54 patients), starting on July 2006 and having a projected duration of 12-13 months; and a two-center final period of at least 70 patients, starting on March 2008 and having a projected duration of 14-15 months.

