# First study period planning

An interim analysis assessing safety data will be conducted after the enrolment of 20 patients. Following the (probable in our opinion) establishment of patient safety, we will be able to extend the study until the enrolment and follow-up completion of 50-54 patients. Based on our pilot period data, we have estimated an HFO-TGI-related improvement in compliance of 25% within days 5-10 (improvement most likely to be confirmed within days 5-8). For alpha = 0.05 and power = 0.80, we will have to enroll 52 patients, whereas the enrollment of 54 patients will raise power to 0.82." Consequently, provided that our pilot data-based prediction is confirmed in the first 20 participants of the first study period, we will conclude that this study period will be adequately powered to assess the evolution of respiratory physiology during

[figure not shown]
the study intervention period. As according to our original hypothesis the evolution of respiratory physiology is a prerequisite for an HFO-TGI-associated improvement in survival, following the aforementioned confirmation, we will add this "intermediate" outcome to the (registered with Clinicaltrials.gov) primary outcome measures of the first study period.

The other primary outcome measure for the first study period will be (as for the whole study) survival to hospital discharge; additional survival assessment time points may include days 28 and 60 post-randomization. The current study period will not be sufficiently powered to reliable assess in-hospital mortality. Nevertheless, regarding 28-day survival, a possible, large chi-square effect size of 0.5-0.6 would result in alpha ≤0.04 and power ≥0.81. This will correspond to a between-group, 28-day survival difference similar to that determined in the Amato trial [i.e. 34% (26)]. However, in such a case, a large difference in 28-day survival will also likely be reflected by a concurrent difference in ventilator-free days (26), which in turn will be explained by early improvements in the respiratory physiology of the HFO-TGI group. Regarding the potential for TGI-associated tracheal mucosal damage (14), this will be assessed as feasible (feasibility to be confirmed during the first period) according to the pre-specified grading of Table 2.

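### A chi-square effect size of 0.5-0.6 does not correspond to a 34-point difference in 28-day survival, so the first-period power statement does not apply to the difference it names

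*Protocol*

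**What the plan says.** The protocol's section on first study period planning concedes that "The current study period will not be sufficiently powered to reliable assess in-hospital mortality". It then turns to 28-day survival and says that "a possible, large chi-square effect size of 0.5-0.6 would result in alpha ≤0.04 and power ≥0.81". The next sentence ties this effect size to a difference in percentage points: "This will correspond to a between-group, 28-day survival difference similar to" the 34% found in an earlier published trial of protective ventilation.

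The size of the period is given under Power Analysis and Study Periods as "a single-center first period of at least 50 patients (average estimate=52 patients, maximum=54 patients", and the planning section repeats the range of 50-54.

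The protocol does not state a control-arm 28-day survival rate, the allocation ratio or the sidedness for this calculation. The Patients section says only that "Randomization will result in assignment to either the control group (treatment with CMV) or the HFO-TGI group".

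**The concern.** For an alive/dead comparison between two arms, the chi-square effect size and the absolute difference are linked by a fixed formula. The protocol gives one figure on each side of that link, and they do not match. The power bound is attached to the effect size, but the following sentence carries it over to 34 points, a smaller effect.

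What is at stake is how a 28-day result from 50-54 patients is read. A reader would take it that the first period has at least 81% power for a difference as large as a published one, so that the risk of missing it is at most 19%. At mid-range mortality that risk is nearer 30%.

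**Working it through.** **Inputs.** From the protocol: effect size 0.5-0.6, alpha 0.04, power 0.81, difference 34 points, N = 50-54. Assumed: 1:1 allocation, a two-sided test on a 2x2 table (1 df), and a range of control mortality.

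**Formulas.** With equal arms and mean rate pbar, w = |p1 - p2| / (2 x sqrt(pbar x (1 - pbar))). Power comes from the noncentral chi-square distribution with 1 df and noncentrality N x w². The critical value at alpha 0.04 is 4.218.

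**Step 1: the plan's own figure.** At w = 0.5 and N = 52 the noncentrality is 52 x 0.25 = 13.

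| w | N = 50 | N = 52 | N = 54 |
|---|---|---|---|
| 0.5 | 0.931 | 0.940 | 0.947 |
| 0.6 | 0.986 | 0.988 | 0.991 |

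The bound of 0.81 is therefore true for the effect size as written, though 0.81 itself is not reproduced. With 1 df it would need w of about 0.40-0.41.

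**Step 2: what 34 points means as w.**

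- 67% against 33%: 0.34 / (2 x sqrt(0.50 x 0.50)) = 0.340, the minimum.
- 52% against 18%: 0.34 / (2 x sqrt(0.35 x 0.65)) = 0.356.
- 40% against 6%: 0.34 / (2 x sqrt(0.23 x 0.77)) = 0.404.
- 34% against 0%: 0.34 / (2 x sqrt(0.17 x 0.83)) = 0.453, the maximum.

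No pair of rates 34 points apart reaches 0.5.

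**Step 3: what w = 0.5-0.6 needs in points.** The smallest difference giving w = 0.5 is 40 points (40% against 0%). It is 44.7 points at control mortality 50%, 48.0 at 60% and 50.0 at 75%. For w = 0.6 the smallest difference is about 53 points, and 60 if the rates are centred on 50%.

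**Step 4: other readings.** Cohen's h for 34 points is at least 0.694 and a goodness-of-fit w at least 0.68, so neither gives 0.5-0.6. With unequal allocation, w is largest when the larger arm has 100% survival: 0.506 at 1:2 and 0.528 at 1:3. The limit is sqrt(0.34) = 0.583, so 0.6 is never reached.

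**Step 5: power for 34 points, two-sided alpha 0.04.**

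| Mortality, control vs HFO-TGI | w | N = 50 | N = 52 | N = 54 |
|---|---|---|---|---|
| 80% vs 46% | 0.352 | 0.669 | 0.686 | 0.703 |
| 67% vs 33% | 0.340 | 0.637 | 0.655 | 0.672 |
| 60% vs 26% | 0.343 | 0.646 | 0.664 | 0.681 |
| 52% vs 18% | 0.356 | 0.680 | 0.697 | 0.714 |
| 50% vs 16% | 0.362 | 0.692 | 0.710 | 0.727 |
| 40% vs 6% | 0.404 | 0.789 | 0.805 | 0.820 |
| 38% vs 4% | 0.417 | 0.815 | 0.830 | 0.845 |

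The 52% row uses the conventional-ventilation 30-day mortality of the earlier HFO trial described in the protocol's introduction. At alpha 0.05 that row becomes 0.712, 0.729 and 0.745.

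The usual normal-approximation formula for two proportions gives values 1 to 3 hundredths higher; at N = 52-54 it reaches 0.81 once HFO-TGI mortality is about 7-9% or less. Fisher's exact test is lower: 0.55-0.58 for 67% against 33% and 0.63 for 52% against 18%, with 26-27 per arm at alpha 0.04. The mirror case, control mortality of about 94% or more, also reaches about 0.81.

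**The case against.** The strongest reply is that the power sentence is not false. It attaches "would result in alpha ≤0.04 and power ≥0.81" to an effect size of 0.5-0.6, and at that effect size power is well above 0.81. This stands. A reader might infer that the power figure is impossible, and the documents do not support that. Even for 34 points, 50-54 patients can reach 0.81 at extreme rates, and the protocol does not state the control rate that would settle it. The 50-80% range for control mortality used here is an assumption.

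How far those extreme rates are plausible can be judged only loosely. HFO-TGI mortality of about 6% would lie far below any mortality quoted in the protocol's introduction, the lowest of which is 26%. That makes the mid-range shortfall the likelier case, but does not prove it.

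A reader might also object that alpha is spoken of as a result of the effect size. That wording is unusual, but a compromise power analysis does return alpha and power together from an effect size and N, and the protocol does not name its method. It does not show an error.

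Finally, the sentence sizes nothing. The 52-54 patients come from the compliance calculation and the trial's 124 from hospital mortality. Day 28 is only a possible additional time point in the first period, and the large effect is put forward as a possibility. This stands too, and limits the weight of the point.

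**Conclusion.** The concern holds for the link between the two figures. Under 1:1 allocation, 34 points corresponds to w = 0.34-0.453 at every base rate and never to 0.5-0.6. The missing control rate does not rescue the text; only allocation of about 1:2 or more unequal, with survival near 100% in the larger arm, would reach 0.5.

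For power the conclusion is conditional. The stated bound overstates the power for 34 points by about 0.08-0.17 if control mortality is 50-80% (0.64-0.73 against 0.81), and not at all at the extreme rates. A reader might infer that the whole trial, or the size of its first period, rests on a wrong calculation. It does not: this is a wrong supporting statement, to be corrected before a 28-day result from the first period is interpreted.

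**What to change.** In the first-period planning section:

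1. Remove the statement that an effect size of 0.5-0.6 corresponds to a 34-point difference. If that effect size is kept, say that it means a difference of at least 40 points, and about 45-50 points for w = 0.5 at mid-range rates.
2. State the assumed control 28-day mortality, the allocation ratio, the test and its sidedness.
3. Restate the power for 34 points at N = 50-54 for that rate. For 52% against 18% with 1:1 allocation, the chi-square approximation gives about 0.68-0.71 at two-sided alpha 0.04, or 0.71-0.75 at alpha 0.05. If Fisher's exact test is intended, use its lower figures.

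The cost is one reworded paragraph and a less favourable stated power. No patients are added and no sample size changes.

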**Figure 1. The proposed sedation protocol.** ARDS, acute respiratory distress syndrome; HFO, high-frequency oscillation; CMV, conventional mechanical ventilation; TGI, tracheal gas insufflation; FiO2, inspired O2 fraction; PEEP, positive end-expiratory pressure.

- \*, PaO2/FiO2<150 mmHg, despite being ventilated at PEEP≥8 cmH2O for >12 consecutive hours.
- †, In both study centers, the standard management of sedation and paralysis of patients with ARDS is similar to the presented protocol.
- ‡, Refers mainly to trauma patients, and/or patients subjected to major surgery.
- §, Defined as presence of spontaneous breathing efforts associated with increases in peak pressure of  $\geq 5$  cmH2O.

- $\parallel$ , At the current ventilatory settings, the pre-specified gas exchange and plateau pressure targets of CMV (see text and Table 1) are achievable for  $\geq$ 60 min after the discontinuation of cisatracurium; in addition, there is no patient-ventilator dyssynchrony.
- \*\*, Restart intravenous sedation according to the fulfillment of  $\geq 1$  of the following criteria: 1) Ramsay score=1; 2) respiratory rate rises to >40/min for >30 min due to patient-triggered breaths; and 3) patient-ventilator dyssynchrony ensues, with or without failure to achieve the pre-specified gas exchange targets of CMV (see text) at the current ventilatory settings.
- ††, These criteria are presented in Figure 4.

[figure not shown]
[figure not shown]

Figure 2 (please see next page for dedicated legend)

- \*, Initiate HFO-TGI if patient fullfils the pre-specified criterion for severe oxygenation disturbance.
- †, Perform 2 ABG analyses within 30 min of HFO-TGI initiation and titrate f and ΔP to a pHa of at least 7.20.
- ‡, High Frequency Ventilator FiO2=1.0 during the Recruitment Period, during the Application of the Additional Recruitment Algorithm, during the 15-min periods that preceded physiologic measurements, and during the 5-min periods of the physiologic measurements. During the Stabilization Period, FiO2 = 80%, 70%, 60% if PaO2/FiO2 of immediately preceding physiologic measurement = 150-200, 200-300, and > 300 mmHg (respectively).
- §, Perform physiologic measurements (arterial and central-venous blood gas analysis and hemodynamics) at that time-point.
- || , Perform physiologic measurements (blood-gas analyses, hemodynamics, and respiratory mechanics with end-inspiratory/expiratory airway occlusion) at that time-point.
- \*\*, Consult immediately with a supervising investigator on how to proceed with the Intervention Failure Algorithm.

ABORT RECRUITMENT MANEUVER IN CASE OF 1) HYPOTENSION: SYSTOLIC PRESSURE < 90 MMHG;
MEAN PRESSURE <60 MMHG; 2) DESATURATION: SPO2 <85% OR ABSOLUTE SPO2 DROP >5%.
IF NECESSARY, TREAT HYPOTENSION AND/OR ASSOCIATED DROP IN CARDIAC OUTPUT WITH FLUIDS AND VASOPRESSORS.
JUST PRIOR TO RETURN TO CMV, A BRIEF ENDOSCOPIC INSPECTION OF THE TRACHEA WILL BE CARRIED OUT.

Abbreviations: CMV, conventional mechanical ventilation; HFO, high-frequency oscillation; TGI, tracheal gas insufflation; CPAP, continuous positive airway pressure; mPaw, mean airway pressure; mPtr, mean tracheal pressure; ΔP, oscillatory pressure amplitude; I:E, inspiratory-to-expiratory time ratio; FiO2, inspired oxygen fraction; ABG=arterial blood gas; SpO2, peripheral oxygen saturation; iNO, inhaled nitric oxide.

**Figure 3. Proposed algorithmic actions and options for the case of Study Intervention Failure.** HFO, high-frequency oscillation; TGI, tracheal gas insufflation; mPaw, mean airway pressure; FiO2, inspired O2 fraction; SpO2, peripheral O2 saturation; iNO, inhaled nitric oxide. An arterial blood gas analysis will be performed and hemodynamic data will be recorded at 30 min after every change in high-frequency ventilator mPaw, or TGI, or use of an additional intervention.

- \*, If applicable, consider HFO without TGI after taking into account the oxygenation response to TGI discontinuation during the weaning period of the preceding HFO-TGI session.
- †, Defined as additional interventions; the use of these interventions will have to be approved by the attending physicians.

- ‡, If applicable, return to the supine position from prone, or discontinue iNO, or both; if on HFO without TGI, restart TGI at its initial setting of 50% of the minute ventilation of the conventional mechanical ventilation that preceded the HFO-TGI session.
- §, If on HFO without TGI, follow all steps of the HFO-TGI protocol (apart from the discontinuation of TGI) as presented in Figure 2.
- $\parallel$ , This time point corresponds to the end of the weaning period of the HFO-TGI session, i.e., 60 min after the reaching of the protocol-pre-specified target mPaw, which is 6 cmH2O lower than the initial mPaw used at the start of the HFO-TGI session (see also Figure 2).

[figure not shown]

Figure 4. Schematic representation of the proposed weaning protocol. CMV, conventional mechanical ventilation;  $FiO_2$ , inspired  $O_2$  fraction; PEEP, positive end-expiratory pressure; pHa, arterial-blood pH; SAP, systolic arterial pressure;  $SpO_2$ , peripheral  $O_2$  saturation. Continuous lines correspond to the clinical evaluation detailed in the dedicated box. For steps I-III, the "transition to the next step" corresponds to successful gradual withdrawal of ventilatory support. The transition from step IV to step V corresponds to a successful spontaneous breathing trial.

- \*, At the end of a successful spontaneous breathing trial confirm that PaO2>60 mmHg and pHa>7.30 by arterial blood gas analysis.
- †, In case of recurrence of respiratory failure, reintubate and consider tracheostomy.
- ‡, In case of patient failure to tolerate spontaneous breathing for 48 consecutive hours, return to Step I or CMV for 12-24 hours; following tracheostomy decannulation, consider interim placement of a minitracheostomy tube to facilitate suctioning of secretions.

TABLE 1. THE CONVENTIONAL VENTILATION STRATEGY

Ventilator mode	Volume assist-control
Target tidal volume (mL/kg predicted body weight) *	6.0 (with allowances from 5.5 to 7.5)
Target end-inspiratory plateau pressure (cm H 2 O)	≤30 (with allowance of up to 35 †)
Ventilator rate (breaths/min) / Target pHa	16-35 / 7.20-7.45
Inspiratory-to-expiratory time ratio	1:2
Combinations of FiO 2 (%) / PEEP (cm $H_2O$ ) $\ddagger$	40 / 5-8; 50 / 8; 60 / 10; 70 / 10-14;
	80 / 14; 90 / 16; 100 / 16-20
Target SpO 2 (%)	90-95
Target PaO 2 (mm Hg)	60-80
Recruitment maneuver §	CPAP of 45 cm $H_2O$ for 20-40 s

FiO2, inspired O2 fraction; PEEP, positive end-expiratory pressure;  $SpO_2$ , peripheral O2 saturation; CPAP, continuous-positive airway pressure. Patients will be ventilated through a 25-26-cm long endotracheal tube with an inner diameter of 8.0-9.0 mm.

- \*, Calculate as " =  $50 + [\text{Height (cm)} 152.4] \times 0.91$ " and as " =  $45.5 + [\text{Height (cm)} 152.4] \times 0.91$ " for males and females, respectively.
- $\dagger$ , Whenever deemed necessary for achieving the lowest target pHa and/or SpO2/PaO2; in such cases, use tidal volumes of 5.5-6.0 mL/kg.
- $\ddagger$ , Whenever the upper limit of the oxygenation targets is exceeded, reduce PEEP at a rate of 1-2 cm  $H_2O$ /hour (and accordingly adjust  $FiO_2$ ) until reaching an  $SpO_2$  of  $\le 95\%$  and/or a  $PaO_2$  of  $\le 80$  mm Hg. During the first 10 days post-randomization, reverse and suspend (for 12 hours) the downward titrations if 1) starting plateau pressure and  $FiO_2$  is  $\le 30$  cm  $H_2O$  and  $\le 70\%$ , respectively; and 2) they are associated with a  $PaO_2/FiO_2$  decrease of >25% and a  $PaO_2/FiO_2$  of <150 mm Hg.
- §, Perform in the control (i.e., the conventional mechanical ventilation) group during the first 4 days after randomization at a rate of 1 every 3-6 hours.

Table 2. Proposed grading of bronchoscopic findings

Grade	Bronchoscopic Findings	Interpretation	Action
I	Pink and glistening tracheal mucosa	Normal; No TGI-related complication	None
II	Reddened and/or swollen mucosa	Probable respiratory infection during mechanical	None
	with/without presence of purulent secretions	ventilation; No TGI-related complication	
III	A. Hemorrhagic mucosa and/or presence of thrombotic material*	Possible mucosal pealing, in conjunction with	Dicontinue
	B. Limited localized necrosis, especially at the carina †, and/or	mechanical erosion of the submucosal vessels by the	TGI §
	presence of necrotic mucosal slough	TGI jet stream; Suggests TGI-related complication §	
	C. Extensive localized necrosis, especially at the carina †, and/or		
	presence of necrotic mucosal slough		

TGI, tracheal gas insufflation.

\*, Any concurrent bleeding diathesis / coagulopathy could constitute an independent contributory factor.

†, Predicted to be probable site of impact of the TGI jet stream.

§, Exception: Grade IIIA findings attributable to tracheostomy performed within the preceding 6-24 hours.
